7.2.1 Subject demographics and other baseline characteristics

Screen failures with SAEs

For screen failed participants in case the participant experienced a serious adverse event during the screening phase the following information is captured and listed: demographic information, informed consent, as well as information on SAEs. Inclusion/Exclusion criteria will be summarized.

Disposition

The following disposition status will be summarized as the number and percentage of participants

- who were screened but not randomized (percentage based on all screened participants)
- who were randomized (percentage based on all screened participants)
- who were randomized but not treated (overall and by reason)
- who were discharged prior to day 15 and day 29
- who completed the study until day 15, day 29, day 45 as well as day 127
- who discontinued treatment prior to day 15,
- who discontinued from study (overall and by the primary reason for discontinuation).

The number and percentage of participants included in each analysis set will be tabulated by treatment group. Participants excluded from an analysis sets will be listed with reasons for exclusion (i.e. including both protocol and non-protocol deviations).

Unless otherwise stated any percentages are based on the respective number of randomized participants.

Demographic and Baseline characteristics

Demographic characteristics, including gender, race, ethnicity, age, age categories (<65 and \geq 65 years), height, body weight at screening, body categories (40 to <60 kg, 60 to <80 kg, 80 kg to <100 kg, 100 kg to <120 kg, $\geq=120$ kg), body mass index (BMI), BMI categories (< 30.0 kg/m² and 30.0 kg/m² to 40 kg/m², $\geq=40$ kg/m²) will be summarized with descriptive statistics by treatment and overall.

A stacked barchart illustrating gender, race and ethnicity will be done. Boxplots will be done for all continuous variables in demographics and baseline characteristics.

Body weight and BMI will be also summarized by time point.

Body mass index (BMI) will be calculated using the following formula:

- $BMI = \text{Body weight (kg)} / [\text{Height (m)}]^2$

The Screening visit height measurement will be used for BMI calculations throughout the study.

The number of days between the onset of symptoms to start of treatment will be listed.

The summary of the following baseline disease characteristics will be provided by treatment group:

- Days from the onset of symptom to randomization
- Days from the onset of symptoms to treatment
- Days from diagnosis to randomization
- Number of days from hospital admission to randomization
- Chest X-ray or CT scan interpretation (Normal/Abnormal/not available)
- Clinical status based on the 9-point ordinal scale (Score=0, 1, ...8)
- Use of corticosteroid at the time of randomization (based on prednisone equivalent dose see [Section 10.7](#))
- Use of anti-coagulants at the time of randomization
- Use of anti-infectives at the time of randomization
- Use of anti-viral treatment at the time of randomization (Yes, No) and by type of anti-viral treatment (e.g. hydroxychloroquine, chloroquine, convalescent plasma, remdesivir, faripivavir, ritonavir, lopinavir)
- Number and presence of the following comorbidities: diabetes, hypertension, cardiovascular disease (i.e. chronic heart disease), chronic lung disease (e.g. COPD, asthma)Baseline Oxygen use based on the type of pulmonary/ventilatory support (defined in [Table 6-1](#))
- Marker for inflammation as continuous variables: CRP, Serum Ferritin, D-Dimer, LDH, neutrophil counts, BNP and troponin.
- A stacked barchart illustrating the percentage of participants by treatment with the number of comorbidities at baseline (0, 1, 2, 3, 4, 5, 6 or more)
- A barchart illustrating the number and presence of the following comorbidities: diabetes, hypertension, cardiovascular disease (i.e. chronic heart disease), chronic lung disease (e.g. COPD, asthma)

The distribution of the three stratification parameters will be summarized separately by treatment group.

For oxygen requirement at baseline the type of support required prior but closest to the day of randomization will be reported.

Protocol deviations will be listed and summarized by treatment group.

All medical history including the comorbidities will be listed.

Randomization information will be listed and summarized by treatment group.

7.2.2 Treatment

Concomitant medications and significant non-drug therapies prior to and after the start of the study treatment will be listed and summarized according to the Anatomical Therapeutic Chemical (ATC) classification system by treatment group. For corticosteroids ATC-Subclasses will be added. Convalescent plasma treatment will be included in the anti-viral treatment presentations.

For any of the below mentioned three treatment categories, if it started prior to treatment and continued during the study, it will be reported under baseline as well as part of SoC during study participation.

A graphical presentation of the cumulative use of different concomitant medications at baseline over the course of the study by treatment group will be provided. For this the cumulative average percentage use will be plotted on the y-axis over the cumulative number of enrolled participants on the x-axis. This presentation will be provided for the following medications:

- Dexamethasone
- Remdesivir
- Hydroxchloroquine or Chloroquine
- Anti-coagulants (using ATC class as provided)

Corticosteroids use

The number and percentage of patients will be summarized by treatment group for the following parameters:

- receiving any corticosteroids after randomization
- receiving Dexamethasone after randomization reporting the highest total daily dose observed during the study using the following ranges:
<6 mg, 6-<12 mg, >= 12 mg

The following presentations will be based on the prednisone equivalent dose (see Appendix for details):

- with a change in their corticosteroids dose after randomization (increased/reduced/stable dose)
- receiving corticosteroids after randomization reporting the highest total daily dose observed during the study using the following ranges:
<7.5 mg, 7.5-<20 mg, >= 20 mg

For subgroup analyses the participants with a high vs. a low corticosteroid dose during the first week following randomization were identified. This was defined as follows:

- Considering any corticosteroid mediation selected by ATC class administered between randomization and the following 7 days (i.e. start date < day 8 and end date > 0).
- Only medication reported with a unit of “mg” was included
- Doses are converted into prednisone equivalent doses applying [Table 10-2](#).
- The total daily dose is derived based in the administration frequency reported in the CRF:
 1. “ONCE”, “QD”, “QID”, “Q24H” – factor 1
 2. “BID” – factor 2
 3. “TID”, “Q8H” – factor 3
 4. “Q6H” – factor 4
- The total dose administered during the first week is derived based on the actual number of days the drug was administered in this period. This is done on a “day” scale, i.e. additional details on administration times are not considered.
- The sum of the total daily doses during the first week in the study is calculated
- The average total daily dose is derived by dividing the sum of the total daily doses by 7.
- A dose of zero is added for any participants not receiving corticosteroids during the first week.
- The average daily prednisone equivalent doses during the first week (dailydose1wk) in mg are categorized as follows:
 - dailydose1wk = 0: “none”
 - dailydose1wk <= 10 (including zero): “<=10”
 - 10 < dailydose1wk <= 20: “>10-20”
 - 20 < dailydose1wk <= 50: “>20-50”
 - 50 < dailydose1wk <= 100: “>50-100”
 - 100 < dailydose1wk <= 200: “>100-200”
 - 200 < dailydose1wk: “>200”

A stacked barchart is provided showing the distribution in these dose categories by treatment group.

- For further subgroup analyses the categories “<=10 mg (Low)” and “>10 mg (High)” are used.

For the medications listed below barcharts on the “counts” use of corticosteroids at baseline by treatment group will be given.

- Dexamethasone
- Methylprednisolone
- Prednisone
- Other

- None

Anti-viral medication use

The number and percentage of patients will be summarized by treatment group for the following parameters:

- receiving any anti-viral medication after randomization
- receiving hydroxychloroquine/chloroquine/remdesivir/faripivavir/ritonavir/lopinavir/convalescent plasma after randomization receiving a combination of the above anti-viral medications after randomization tabulated by all combinations actually occurring.

For the medications listed below barcharts on the “counts” use of anti-virals at baseline by treatment group will be given.

- Azithromycin
- Hydroxychloroquine
- Remdesivir
- Convalescent plasma
- Immunoglobulin G human
- Other
- None

For convalescent plasma and immunoglobulin G human, also consider them as baseline records if any participant had them administered before screening/baseline visit.

Anti-coagulation therapy

The number and percentage of patients will be summarized by treatment group for the following parameters:

- receiving any anti-coagulation medication after randomization

The “counts” at baseline will be displayed in a barchart.

• Anti-infectives therapy

The number and percentage of patients will be summarized by treatment group for the following parameters:

- receiving any anti-infectives medication after randomization

The “counts” at baseline will be displayed in a barchart.

Combination of SoC medications

The number and percentage of patients receiving any combination of steroids, anti-viral, anti-infectives and/or anti-coagulants treatments after randomization will be summarized by treatment group.

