6.2.2 Descriptive analyses

CRP and ferritin

Panels of individual spaghetti plots over time for CRP and ferritin will be provided using a logscale. The profiles of all participants in the respective treatment group will be included in these graphs as grey lines in the background and the respective individual participants profile will be plotted with darker color in the foreground. The respective applicable normal ranges will be added and it will be indicated by a symbol if a patient died.

Survival without the need for invasive mechanical ventilation

The numbers and percentages of responders will be calculated up to Day 15 and up to Day 29 respectively. It will be presented by treatment group together with the difference in response rates.

Improvement in clinical status

The numbers and percentages of responders will be calculated up to Day 15 and up to Day 29 respectively. It will be presented by treatment group together with the difference in response rates and a two-sided 90% CI based on Fishers exact test.

In addition a shift table of changes in response status will be provided with weekly time intervals (e.g. baseline, week 1, week 2, week 3 and week 4). For this the following response categories will be included:

- improvement of at least 1 step from baseline,
- no change from baseline
- worsening from baseline.

Also a stacked barchart illustrating the percentage of participants in each response categories as outlined above will be provided. Treatment groups will be presented next to each other. This will be provided for weeks 1, 2, 3 and 4.

For the subgroup analysis a shift table and stacked barchart for subgroup of participants with high baseline CRP by high and low corticosteroid dose during week 1 will be provided.

Clinical status over time

The 9-point ordinal scale will be summarized (mean, median, standard deviation, minimum, maximum, frequencies and percentages in each category) will be summarized by visit (including a time point for data from early discharge) and treatment group.

A stacked barchart illustrating the percentage of participants for each category of the 9-point ordinal scale with one bar will be provided. Treatment groups will be presented next to each other within one category. This will be provided for Day 8, Day 15, Day 21 and Day 29 (labeled as weeks 1, 2, 3 and 4).

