6.2.3 Statistical model, assumptions and hypotheses

CRP and ferritin

CRP levels are assumed to follow a log-normal distribution. Thus the log-transformed CRP data will be analyzed by fitting an MMRM model. Treatment, visit and their interaction as well as the three stratification factors will be included as fixed factors and baseline CRP as a covariate. Interactions between visit and each of the terms in the model will also be included. To model the dependency of observations an unstructured variance-covariance matrix will be fitted.

The analysis will be performed on the PD analysis set. The back-transformed geometric means for both treatment groups as well as the geometric mean ratios (MAS825 vs placebo) will be reported together with 90% confidence intervals (CIs) for each visit. The 1-sided p-value for the overall treatment factor will be reported. Ferritin levels will also be analyzed in the same manner.

For the subgroup analysis the same model as for the original MMRM analysis including in addition a factor for high vs. low corticosteroid use during week 1 (see [Section 7.2.2](#) for details) and its 3-way interaction with treatment and visit. The geometric means (+/-SE) per corticosteroid category and treatment group as well as the ratio of geometric mean (90% CI) per corticosteroid group are reported for each visit.

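### The High/Low corticosteroid subgroups are defined by doses given after randomisation, so MAS825-versus-placebo contrasts within them are not randomised comparisons

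*SAP*

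**What the plan says.** SAP 7.2.2 sets up the subgroup: "For subgroup analyses the participants with a high vs. a low corticosteroid dose during the first week following randomization were identified". The rules are:

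- **Window.** Any corticosteroid "administered between randomization and the following 7 days (i.e. start date < day 8 and end date > 0") counts. This takes in courses already running at randomisation and courses started up to Day 7.
- **Averaging.** "The average total daily dose is derived by dividing the sum of the total daily doses by 7". Non-users are kept: "A dose of zero is added for any participants not receiving corticosteroids during the first week".
- **Cut.** "For further subgroup analyses the categories “<=10 mg (Low)” and “>10 mg (High)” are used".

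The class is used in three places:

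- **SAP 6.2.3.** The CRP and ferritin subgroup analysis repeats the main MMRM, "including in addition a factor for high vs. low corticosteroid use during week 1", with its three-way interaction with treatment and visit. It reports the MAS825/placebo ratio with a 90% CI for each steroid class at each visit.
- **SAP 7.2.3.** The same structure is applied to body temperature in the high-baseline-CRP group, with mean differences and 90% CIs per class.
- **SAP 6.2.2.** Clinical status gets a "shift table and stacked barchart for subgroup of participants with high baseline CRP by high and low corticosteroid dose during week 1".

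A pre-randomisation measure exists. SAP 7.2.1 lists among the baseline characteristics "Use of corticosteroid at the time of randomization (based on prednisone equivalent dose", with conversion factors in SAP 10.7. It does not define the subgroup. The visible text gives no caveat that the within-class comparisons are non-randomised.

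**The concern.** Protocol 6.2.1 lets sites give corticosteroids for COVID-19 before and during the study as local standard of care, on medical judgement. SAP 7.2.2 itself tabulates dose increases and reductions after randomisation. Week-1 dose can therefore respond to how a participant fares after the infusion.

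Suppose MAS825 helps and sicker participants get more steroid. Fewer MAS825 participants are then escalated. Those who still reach High are sicker than the placebo participants in High, while Low gains MAS825 participants who would have been High on placebo. Both classes then compare a sicker MAS825 group with a healthier placebo group, and the estimated benefit shrinks in both.

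Two features of the derivation add to this. Steroids given up to Day 7 classify outcomes measured on Days 2, 4 and 6, so later treatment sorts earlier results. The divisor of 7 is fixed, with no stated adjustment for death or discharge, so an early exit pushes a participant towards Low.

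At stake is how the per-class ratios and differences are read. With confidence intervals attached, they look like the effect of MAS825 with and without meaningful steroid exposure, and part of any pattern could come from the grouping.

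**Working it through.** **1. The plan's own CRP figures.** Protocol 12.9.2 gives 60 per arm, a 44% greater reduction, CV 130%, one-sided alpha 1% and power 80%.

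- Log-scale SD = sqrt(ln(1 + 1.3²)) = 0.995
- Effect = −ln(0.56) = 0.580
- z = 0.580 / (0.995 × sqrt(2/60)) − 2.326 = 0.87, so power is 80.7%. The stated 80% reproduces.

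The protocol's assumed clinical effect (12.9.1) is 3.6/9.2 = 0.39 SD of APACHE II.

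**2. How easily the class moves.** SAP 10.7 converts dexamethasone at 20/3. For an illustrative 6 mg/day, the prednisone equivalent is 6 × 20/3 = 40 mg. One day in the window averages 40/7 = 5.7 mg (Low); two days average 80/7 = 11.4 mg (High). One extra day of treatment changes the class.

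**3. Illustrative simulation.** The documents give neither the link between steroid dose and severity nor the effect of MAS825 on steroid use, so the following are assumptions:

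- Severity S ~ N(0, 1)
- Week-1 severity W = S + N(0, SD 0.5) − c × (MAS825), with c = 0, 0.39, 0.5 or 1.0
- P(High) = logistic(k × W), with k = 1 or 2
- Log baseline CRP = 0.7 S + N(0, SD 0.7)
- Log follow-up CRP = 0.7 S + N(0, SD 0.7) + direct effect × (MAS825). The SD is sqrt(0.49 + 0.49) = 0.99, close to the plan's 0.995
- Analysis: log CRP on treatment, class, their interaction and log baseline CRP

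MAS825/placebo ratios within class, from 4,000,000 simulated participants:

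| c | k | P(High), placebo → MAS825 | True ratio 0.56: High / Low | No direct CRP effect: High / Low |
|---|---|---|---|---|
| 0 | 1 or 2 | 50% → 50% | 0.56 / 0.56 | 1.00 / 1.00 |
| 0.39 | 1 | 50% → 42% | 0.57 / 0.57 | 1.02 / 1.02 |
| 0.39 | 2 | 50% → 39% | 0.59 / 0.59 | 1.05 / 1.05 |
| 0.5 | 1 | 50% → 40% | 0.58 / 0.58 | 1.03 / 1.03 |
| 0.5 | 2 | 50% → 36% | 0.60 / 0.60 | 1.07 / 1.06 |
| 1.0 | 1 | 50% → 31% | 0.60 / 0.59 | 1.06 / 1.06 |
| 1.0 | 2 | 50% → 24% | 0.65 / 0.63 | 1.15 / 1.12 |

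The overall ratio stays at 0.56 or 1.00 throughout. Without the baseline covariate, c = 0.5 to 1.0 gives 0.59 to 0.71 in High and 0.59 to 0.68 in Low. Baseline CRP thus removes a good part of the bias but not all of it, because the selection happens after baseline.

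**4. Would the planned chart of dose categories by arm show the problem?** Not reliably. Take an outcome with no true treatment effect and 60% High in both arms. Let steroid dose correlate 0.5 with severity on placebo and 0 on MAS825. The spurious MAS825-minus-placebo difference, without covariate adjustment, is then −0.32 SD in High and +0.48 SD in Low. Equal class sizes do not rule out bias.

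**The case against.** The strongest reply concerns weight, and much of it stands.

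- **Scope.** The factor does not enter the primary APACHE II ANCOVA (SAP 6.1.3), its sensitivity analysis (6.1.4) or the main CRP and ferritin MMRM (6.2.3). Body temperature is labelled exploratory, and the clinical-status outputs are descriptive, without a model or test. No visible objective asks whether MAS825 adds to steroids, and no visible decision rule rests on these subgroups. All of this is correct. Parts of SAP 6.1.10 are redacted, so the APACHE II subgroup model is not judged.
- **Adjustment.** The SAP model includes baseline CRP and the stratification factors. This reduces the bias, as shown, but cannot remove selection that arises after baseline.
- **The class is partly a baseline feature.** Courses already running at randomisation count. If few participants change dose in week 1, the bias is small. The documents do not give that share.
- **A baseline definition asks a different question.** It classes participants first given steroids after randomisation as Low, and their number is unknown. This is a real cost, but the resulting contrast is between randomised groups.

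A reader might also infer that an inert drug could appear harmful in these subgroups. The reasoning does not support that: an inert drug does not alter steroid use, and the c = 0 row shows no bias. Ratios above 1 arise for a drug that lowers steroid need but has no direct effect on CRP. That is a special case here, since protocol 4.1 treats CRP as a key marker of inflammasome inhibition.

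**Conclusion.** The concern holds for the subgroup outputs. The High/Low class is partly determined after treatment, and the within-class contrasts in SAP 6.2.3 and 7.2.3 are not randomised comparisons. Bias requires two conditions together: MAS825 changes who receives steroids or how much, and steroid dose is related to prognosis. Both are plausible when steroids are given on medical judgement, but the documents quantify neither.

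The actual size is unknown. Under the stated assumptions, with severity effects of 0.39 to 1.0 SD and baseline CRP adjustment, a true ratio of 0.56 is estimated as about 0.57 to 0.65. A true ratio of 1.00 becomes about 1.02 to 1.15. At the protocol's own 0.39 SD the distortion is modest: 0.57 to 0.59, and 1.02 to 1.05. The upper end needs a 1.0 SD effect within the first week and the steeper steroid slope. The simulation uses one visit and omits the stratification factors, so it indicates direction and order of size rather than predicting the MMRM output.

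It would go too far to conclude that these contrasts are always biased, or that the trial's primary or main secondary results are compromised. The documents support neither.

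**What to change.** In SAP 7.2.2, 6.2.2, 6.2.3 and 7.2.3, define High/Low by prednisone-equivalent daily dose at randomisation, with the same 10 mg cut, wherever MAS825 is compared with placebo. SAP 7.2.1 already summarises steroid use at that time point, and the conversion table in SAP 10.7 applies unchanged.

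Keep the week-1 split only as a descriptive display, labelled as post-randomisation and not interpretable as a treatment effect.

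The cost is a wording change and one re-derived flag from data already collected. The small downside is that participants who first receive steroids after randomisation count as Low; the descriptive week-1 display would still show them. Nothing changes in how participants are treated.

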10.7 Steroid conversion factors

Steroids will be displayed using prednisone equivalent doses. The doses displayed in the following table are considered equivalent. To determine prednisone equivalent doses, doses (in unit mg) will be multiplied by the conversion factor shown in [Table 10-2](#). In case multiple corticosteroids are used at a certain visit the prednisone equivalent doses will be added up to obtain the total prednisone equivalent dose.

Table 10-2 Steroids conversion factors

WHO drug code	Preferred Term Corticosteroid	Equivalent Dose [mg]	Conversion Factor
000447xx	Prednisone	5	1
000162xx	Prednisolone	5	1
000496xx	Methylprednisolone	4	1.25
012428xx	Meprednisone	4	1.25
001867xx	Prednylidene	5 5/7	0.875
000319xx	Triamcinolone	4	1.25
000146xx	Cortisone	25	0.2
000286xx	Hydrocortisone	20	0.25
002131xx	Fludrocortisone	2	2.5
000085xx	Betamethasone	0.75	20/3
000664xx	Paramethasone	2	2.5
000160xx	Dexamethasone	0.75	20/3
008827xx	Deflazacort	6	5/6

Commercially Confidential Information

Commercially Confidential Information

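### SAP 7.2.2 counts only steroid records in mg towards the week-1 dose, with no conversion of other mass units, so a systemic steroid entered in g contributes nothing and its recipient may be filed as Low

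*SAP*

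**What the plan says.** SAP 7.2.2 (Treatment, Corticosteroids use) builds the week-1 dose as follows.

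- **Selection.** Any corticosteroid identified by ATC class is taken if its dates overlap the week after randomization ("i.e. start date < day 8 and end date > 0").
- **Unit filter.** The rule opens "Only medication reported with a unit of" and then names mg. No other unit is mentioned and no conversion is given.
- **Equivalence.** SAP 10.7 supplies the factors: "To determine prednisone equivalent doses, doses (in unit mg) will be multiplied by the conversion factor shown in" Table 10-2.
- **Sum and average.** "The total dose administered during the first week is derived based on the actual number of days the drug was administered in this period". Then: "The average total daily dose is derived by dividing the sum of the total daily doses by 7".
- **Zero rule.** "A dose of zero is added for any participants not receiving corticosteroids during the first week".
- **Cut.** "For further subgroup analyses the categories" are Low at 10 mg or less and High above 10 mg.

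The High/Low factor is used in the CRP and ferritin subgroup MMRM (SAP 6.2.3), the body-temperature subgroup MMRM (SAP 7.2.3), and the subgroup shift tables and bar charts for clinical status (SAP 6.2.2).

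**The concern.** The filter acts on the unit in which a dose was written, not on the drug, its route or its amount. Two participants given the same systemic dose can land in different categories because one site typed 1000 mg and another typed 1 g. An entry in g is a valid unit, so it need not trigger a data query.

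The zero rule does not settle what happens next. It covers participants not receiving steroids and is silent on those who received them but have no mg record. Such a participant either carries a sum of zero, and so appears as none and as Low, or has no category at all. On the first reading the outputs disagree: the SAP 7.2.2 count of participants given any corticosteroid after randomization carries no unit filter, so the same person could be treated in that table and untreated in the dose bar chart.

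At stake is the steroid subgroup question. Heavily treated participants placed in Low would blur the contrast between the categories. If the affected numbers differed between arms, the treatment comparison within a category would be affected too.

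**Working it through.** The plan states no figure on this point, so there is none to reproduce. I applied the SAP algorithm to example regimens. The regimens are assumptions chosen only to exercise the rule; neither document mentions a 1 g dose.

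**Inputs**
- Conversion factor = 5 / equivalent dose (SAP Table 10-2). Methylprednisolone: 5/4 = 1.25. Hydrocortisone: 5/20 = 0.25. Dexamethasone: 5/0.75 = 20/3. These agree with the printed factors.
- Divisor 7 and cut at 10 mg/day (SAP 7.2.2). The cut therefore equals a week-1 sum of 7 × 10 = 70 mg prednisone equivalent.

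**Formula:** average daily dose = sum of (dose in mg × conversion factor × frequency factor × days given) / 7. All examples are given once a day (frequency factor 1).

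| Assumed week-1 record | All mass units converted | SAP rule as written |
|---|---|---|
| Methylprednisolone 1 g, 1 day, entered in g | 1000 × 1.25 / 7 = 178.6 (>100-200, High) | 0 (none/Low, or no stated category) |
| Methylprednisolone 1 g, 3 days, entered in g | 1000 × 1.25 × 3 / 7 = 535.7 (>200, High) | 0 (none/Low, or no stated category) |
| 1 g, 1 day, in g, plus 40 mg, 1 day, in mg | (1250 + 50) / 7 = 185.7 (>100-200, High) | 50 / 7 = 7.1 (Low) |
| 1 g, 1 day, in g, plus 40 mg, 6 days, in mg | (1250 + 300) / 7 = 221.4 (>200, High) | 300 / 7 = 42.9 (>20-50, High) |

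**Direction.** Dropping a record removes a non-negative term from the sum, so the computed dose can only fall. With mixed units the High/Low class changes only if the part recorded in mg is 70 mg or less and the full sum exceeds 70 mg. The finer dose categories can change more often, as the last row shows.

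**How large a dropped dose must be.** With nothing else recorded, a week-1 total above 70 / 1.25 = 56 mg (0.056 g) of methylprednisolone, or above 70 / 0.25 = 280 mg (0.28 g) of hydrocortisone, belongs in High.

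**Micrograms.** At the largest factor in Table 10-2 (20/3), 500 micrograms a day is 0.5 × 20/3 = 3.3 mg/day, which cannot cross the cut alone. Grams are where the category is at risk.

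**Size of the cells.** The body-temperature and clinical-status subgroup outputs keep only participants with baseline CRP above the median, so at most about 60 of the planned 120. Two arms by two steroid classes give four cells. If evenly filled (an assumption), that is 60 / 4 = 15 each, and one misfiled participant is 1/15, about 7% of a cell.

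**The case against.** The best defence is that the filter has a purpose. Selection is by ATC class, Protocol 6.2.1 permits inhaled and topical steroids, and Table 10-2 lists substances without routes. A mg-only rule may have been meant to keep out non-systemic products, and converting every microgram record could count an inhaled dose as systemic. That stands as a warning about the remedy, but it does not rescue the rule. The SAP does not state this purpose, and unit is a poor stand-in for route: an inhaled product entered in mg is counted and a systemic one entered in g is lost. The SAP converts units with care elsewhere (10.1 for laboratory values, 7.2.5 for urea and creatinine).

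It is also true that Protocol 11.2 provides queries for discrepancies and missing values, and that all concomitant medication is listed. A missing unit may therefore be caught and a dropped record stays visible in listings. Neither puts the dose into the sum.

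A reader might go further and infer that "dividing the sum of the total daily doses by 7" understates the dose of participants discharged within the week. The documents do not support that. The window is 7 days. Protocol 8.2.2 records medication changes throughout participation, Protocol 6.2.1 asks discharged participants to report new medicines, and the Day 15 contact collects them (Table 8-1, footnote 3). For anyone followed all week, 7 is the correct divisor. Only death or withdrawal before Day 7 with a sum of 70 mg or less could change the class, and averaging over the window or over days alive is then a matter of definition.

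**Conclusion.** The point holds as a gap in the derivation. The rule as written gives a wrong dose for any systemic steroid recorded in g, always too low, and leaves the class of a participant with only such records undefined or Low. In the example the shortfall is 178.6 mg/day against a cut of 10.

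The consequence is limited. The factor enters subgroup outputs only. The primary ANCOVA (SAP 6.1.3) does not use it, and the success criterion does not depend on it. SAP 6.1.10 also mentions subgroup analyses of APACHE II, but the redactions hide whether the steroid class enters them, so I make no claim there.

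Two stronger readings are not supported. A reader might infer that participants have in fact been misfiled, but the documents give no count of records in other units, so the most that can be said is that they may be. A reader might also infer that the loss falls mainly on pulse doses because those tend to be written in grams; neither document says how such doses are recorded.

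**What to change.** Amend SAP 7.2.2 before database lock:

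1. State that the week-1 derivation uses systemic corticosteroids only, identified by route, or by the ATC subclasses that SAP 7.2.2 already adds if route is not collected.
2. For those records, convert g and micrograms to mg before applying Table 10-2.
3. Class a participant whose only records have missing or non-convertible units as not classifiable, not as zero. Reserve zero for participants with no systemic steroid record in the window.
4. Where non-convertible records sit beside usable ones, list them. High is secure once the usable part exceeds 70 mg.
5. Report the numbers of records and participants converted and not classifiable, by treatment group.

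The divisor of 7 can stay. The cost is a unit-conversion step, a route condition, one extra category and a short count table. No new data are needed if route or ATC subclass is already held; the documents do not show whether route is collected.
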